PreActiv’s digital prehabilitation platform has been developed over the last two years by physicians, exercise physiologists, physiotherapists, software engineers, front-end developers, graphic designers, accessibility experts, and members of the public. PreActiv’s digital prehabilitation platform provides tailored, progressive, dynamic, evidence-based prehabilitation to patients within their own home via their computer, smartphone, or tablet. Exercise prescriptions are tailored to the patient’s mobility level and fitness level, which are assessed via in-platform questionnaires and functional assessments. Subsequently, patients are enrolled onto an easy-to-follow programme of vigorous intensity aerobic and resistance exercise, plus breathing exercises in three 35-minute sessions per week for six weeks. The programme is adapted iteratively based on the patient’s fortnightly exercise test results, further tailoring the course to their needs and aiming to progress the intensity of the exercises over time. Within PreActiv’s digital prehabilitation platform, patients are enrolled into a managed community forum of patients and healthcare professionals where they can post their achievements and questions. Alongside access to

PreActiv's digital platform, patients will be given educational materials that summarise the benefits of prehabilitation and how to realise them. At the end of the programme, patients are given a certificate and report which details their progress.

The novel provision of tailored, progressive, dynamic, evidence-based, and home-based prehabilitation via a digital platform requires evaluation for feasibility, prior to a larger study investigating the efficacy of PreActiv's digital prehabilitation platform to improve preoperative fitness and postoperative outcomes.

2. Aims

The primary aim of this study is to evaluate the feasibility of PreActiv's digital prehabilitation, prior to a future larger study investigating its efficacy. The following outcomes measures will be evaluated during the study:

- Recruitment rate (the proportion of patients invited that provide written informed consent)
- Uptake (the proportion of patients invited that are willing to be screened for eligibility)
- Screen-pass rate (the proportion of willing patients that pass screening for eligibility)
- Adherence (the proportion of exercise sessions offered that are attended)
- Compliance (the proportion of exercise sessions that are completed as prescribed)

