- Retention (the proportion of patients that enrol into the study who complete follow-up measurements)
- Safety (the incidence and severity of adverse events)
- Acceptability (Likert scale and open-ended survey questions, posts in community forum)

The secondary aim is to assess the preliminary efficacy of PreActiv's digital prehabilitation by measuring pre- to post-intervention changes to:

- Cardiorespiratory fitness ($VO_{2\text{PEAK}}$, ventilatory threshold)
- Functional fitness (1-minute sit-to-stand test, 1-minute seated push-up test)
- Resting blood pressure and heart rate
- Self-reported physical activity level (International Physical Activity Questionnaire Short Form)
- Quality of life (EuroQoL EQ-5D-5L Scale)
- Mood (Hospital Anxiety and Depression Scale)

An exploratory aim is to evaluate the economic/environmental impact of PreActiv's digital prehabilitation:

- Cost per patient to deliver PreActiv's digital prehabilitation, with comparison to published costs for face-to-face and telemedicine prehabilitation programmes

- Environmental impact avoided by performing prehabilitation at home via PreActiv's digital prehabilitation compared to the estimated hypothetical emissions associated with participants travelling to the hospital three times per week for six weeks for face-to-face prehabilitation.

3. Study design

A single-arm pilot study conducted at the Royal United Hospitals Bath NHS Foundation Trust (RUH). All participants will be allocated to receive PreActiv's digital prehabilitation alongside usual care. Usual care at the RUH involves a digital preoperative assessment of surgical risk and relevant investigations such as electrocardiogram (ECG) and blood tests for all patients. For some patients, usual care may also include seeing an anaesthetist (depending on their risk factors) and seeing other allied healthcare professionals, e.g., dietician (depending on their individual requirements or the nature of the surgery). Prehabilitation is not standard of care at the RUH. Pre-intervention testing will be conducted in week 0 and post-intervention testing will be conducted in week 7.

4. Participant eligibility

The following inclusion criteria will define patients eligible for the study:

- Planned for major elective surgery ≥ 10 weeks from time of recruitment

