 - Major or complex surgery examples in NICE guideline NG45 'Routine preoperative tests for elective surgery' provides appropriate examples that are relevant to the patient cohort at RUH. We have extrapolated from these examples a list of surgical procedures that qualify as major or complex surgery and are carried out at the RUH. This list is not exhaustive but provides a range of procedures that are applicable for example: laparotomy, joint replacement, total abdominal hysterectomy, nephrectomy, neck dissection, parotidectomy, endoscopic resection of prostate, thyroidectomy.
- Aged ≥ 50 years

Subgroups of patients will be excluded:

- Surgery scheduled in <10 weeks
- Any relative or absolute contraindications to undertake an exercise test as described by the American College of Sports Medicine (ACSM, 2022) and the American Heart Association (Fletcher et al., 2013)
- Unsuitable to increase physical activity level as determined by Physical Activity Readiness Questionnaire (PAR-Q)
- Uncontrolled or poorly-controlled lung condition, diabetes, or seizures
- Recent (<12 months) cardiovascular events needing hospital admission
- Ongoing infection or wound making this programme hazardous for the patient
- Unable to access technology required to use the PreActiv digital platform

- Currently meeting World Health Organisation (WHO) physical activity guidelines of 75-300 minutes of moderate to vigorous intensity physical activity per week, plus twice-weekly muscle strengthening activities
- Unable to understand explanations and/or provide informed consent
- Unable to understand written or spoken English, and without ongoing access to an interpreter
- Any condition and/or behaviour that would pose undue personal risk or introduce bias into the study
- Currently enrolled in another research trial

5. Study procedures

a. Sample size

A sample size of $N = 34$ has been selected, based on the primary aim of this pilot study to determine whether progression to a full-scale study is indicated, according to predefined progression criteria. Methodology for sample size estimation in external pilot studies published by Lewis et al. (2021) has been used to inform the sample size. A traffic light system (Avery et al., 2017) has been used to define progression criteria based on two key outcome measures - adherence and retention:

	Red stop	Amber amend	Green go
Adherence	0-50%	51-74%	75-100%
Retention	0-50%	51-74%	75-100%

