The prehabilitation programmes are personalised to cater for differing mobility and fitness requirements and adapt on a fortnightly basis in line with the patient's progress. [REDACTED]

[REDACTED]

Exercise dose

All prehabilitation programmes consist of three ~35-minute sessions per week for a six-week period (Table 2). Rest days will be encouraged throughout the programme to facilitate recovery and reduce the likelihood of injury. Previous studies have found that six weeks of prehabilitation with three sessions per week improved 1-minute sit-to-stand test performance (Bradley et al., 2023), $\dot{V}O_{2\text{PEAK}}$ and ventilatory threshold (West et al., 2015). A multimodal approach to fitness will be taken, with each of the three sessions having an aerobic, resistance, and respiratory component, as recommended in the best practice guidelines for preoperative exercise (Tew et al., 2018).

Exercises will be performed in a vigorous-intensity circuit-training format utilising body-weight and light external resistance. Previous research has shown circuit training with body-weight and dumbbell exercises reduced postoperative outcomes and length of hospital stay following elective abdominal aortic aneurysm repair (Barakat et al., 2016).

The training sessions will commence with a 5-minute warm-up of dynamic mobility exercises performed at light intensity (rating of perceived exertion (RPE) 2-3/10 on a Borg CR10 scale) (Arney et al., 2019, Garber et al., 2011). Next, participants will complete aerobic exercise training for three sets of five exercises, where exercises are performed for 40 seconds followed by 20 seconds of passive rest, with a 50-second passive rest between sets. After completing aerobic exercise training, participants will be guided through resistance training for major muscle groups, utilising bodyweight and light external resistance (e.g., food tins, water bottles) for two sets of five exercises, where exercises are performed for 40 seconds followed by 20 seconds of passive rest, with a 50-second passive rest between sets. The target intensity for both aerobic and resistance exercise is vigorous-very vigorous, defined as RPE $\geq 5/10$ on a Borg CR10 scale (Arney et al., 2019, Garber et al., 2011). Finally, participants will complete two respiratory muscle training exercises for a total of ~4 minutes.

[figure not shown]

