- **Compliance:** If participants report an RPE <5 for aerobic and/or resistance exercise on two occasions, they will be telephoned by a researcher to assess why they have scored their RPE <5. If poor technique or lack of understanding is causing RPE <5, education on the importance of intensity and how to achieve higher intensities will be provided. If technique/understanding are not the issue, and the programme is too easy, the course would be adapted manually (in the future, the adaptation of the course would be partially automated).

Non-exercise intervention

General advice and information on services relating to alcohol consumption, smoking, and nutrition will be provided in the PreActiv eBook. Specific instruction or advice on alcohol, smoking, and nutrition is beyond the scope of this iteration of the PreActiv digital platform but will be included in subsequent versions.

A community forum will be provided within the PreActiv digital platform, which will allow people undergoing similar surgeries to share experiences, discuss queries, and seek support from peers. Participants will have access to the community forum throughout their prehabilitation programme, and for one month post-surgery, to allow participants to share comments about their surgery and recovery experience. All comments made in the community forum will be archived for later analysis in order to further refine and evaluate PreActiv's digital prehabilitation.

There will be a check-in session on a Monday with a member of the research team via the community forum so users can access health professional support. This support is included in the implementation plan and is part of the intervention.

d. Measurements

Primary outcome measurements will be collected throughout the study (week 0-7).

Feasibility

- Recruitment rate: the proportion of patients invited that provide written informed consent
- Uptake: the proportion of patients invited that are willing to be screened for eligibility
- Screen-pass rate: the proportion of willing patients that pass screening for eligibility
- Adherence: the proportion of exercise sessions offered that are attended, assessed based on the number of sessions completed on the PreActiv platform (note: subsequent exercise sessions only become available to participants once they have watched the previous video).
- Compliance: the proportion of exercise sessions that are completed as prescribed:

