 - Exercise intensity: comparing the RPE reported by participants to the target RPE prescribed (i.e., RPE 5-10/10 is the target, so RPE 6/10 would be compliant but RPE 4/10 would be non-compliant). The proportion of aerobic and resistance sessions that are completed at the target intensity will be reported. It has been shown that an RPE score reported at the end of an exercise session is equivalent to the average RPE reported after each exercise (Day et al., 2004).

- Exercise type: after each session, participants will respond to the question: “how much of the session could you complete?” with options: all / most / some / none. If they select any option other than “all”, they will be asked to identify any exercises included in their session that they couldn’t complete from a list. Any sessions where ≥ 1 exercise was not completed will be deemed non-compliant to the type of exercise prescribed. The proportion of sessions where all exercises are completed will be reported.
- Duration: after each session, participants will respond to the question: “how much of the session could you complete?” with options: all / most / some / none. If they select any option other than “all”, they will be asked to identify any exercises included in their session that they couldn’t complete from a list. If they do not select any specific exercise, then we infer that participants were unable to perform the exercises for the required duration. Any sessions where most / some / none is reported with no specific exercise identified will be deemed non-compliant to duration. The proportion of sessions where exercises were performed for the target duration will be reported.
- Retention: the proportion of patients that enrol into the study who complete follow-up measurements
- Safety: the incidence and severity of adverse events reported during the weekly check-in session with a member of the research team, and via a free-text response box after each exercise session to be completed if the participant indicates that they could not perform all exercises.

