 - 1-minute testing protocols have been selected to increase the emphasis on measuring endurance rather than muscular strength, due to the associations between cardiorespiratory fitness and surgical outcomes. The 1-minute sit-to-stand test has been shown to induce similar cardiorespiratory responses as cardiopulmonary exercise testing in COPD patients (Gephine et al., 2020), and has been implemented in prehabilitation trials (Bradley et al., 2023). The 1-minute seated push-up test is a relatively novel assessment, and has been shown to correlate with other functional fitness measures (Chokphukiao et al., 2023, Poncumphak et al., 2023).
- Self-report physical activity: Participants will complete the IPAQ short-form questionnaire to self-report days per week and minutes per day of vigorous intensity physical activity, moderate intensity physical activity, walking, and sitting. 'MET-hours' (MET = metabolic equivalent of task) per week will be calculated. This information will be compared to the WHO guidelines on physical activity and sedentary behaviour.

Psychological assessments

- Quality of life: Participants will complete the EQ-5D-5L to provide insights into mobility, self-care, usual activities, pain/discomfort, and anxiety/depression.
- Mood: Participants will complete the Hospital Anxiety and Depression Score

Economic & environmental

- Cost per patient to deliver PreActiv's digital prehabilitation, with comparison to published costs for face-to-face and telemedicine prehabilitation programmes
- Environmental impact avoided by performing prehabilitation at home via PreActiv's digital prehabilitation compared to the estimated hypothetical emissions associated with participants travelling to the hospital three times per week for six weeks for face-to-face prehabilitation. Publicly-available carbon emissions data will be used for calculations.

e. Data analyses

The primary aim of this study is to test feasibility of the PreActiv's digital prehabilitation. Feasibility will be assessed by reporting proportions and comparing to predefined progression criteria (for adherence and retention). This pilot study is not adequately-powered to investigate the statistical significance of pre- to post-intervention changes to secondary outcome measures. As such, data analyses will be predominantly descriptive. Effect sizes will be reported to convey the magnitude of pre- to post-intervention changes to secondary outcomes.

6. Patient and public involvement (PPI)

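### Does an undefined 'sessions offered' denominator let participants who stop early pass the adherence progression criterion?

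*Combined protocol and SAP*

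**What the plan says.** Section 5a (Sample size) says a traffic-light system "has been used to define progression criteria based on two key outcome measures - adherence and retention". The bands are the same for both outcomes: red 0-50%, amber 51-74%, green 75-100%.

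Section 5d (Measurements, Feasibility) defines adherence as "the proportion of exercise sessions offered that are attended, assessed based on the number of sessions completed on the PreActiv platform". A note in the same bullet adds that "subsequent exercise sessions only become available to participants once they have watched the previous video". Section 2 (Aims) gives the same definition without the note. Neither place gives a number of sessions.

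The dose is in section 5c (Exercise dose): "All prehabilitation programmes consist of three ~35-minute sessions per week for a six-week period". Retention is "the proportion of patients that enrol into the study who complete follow-up measurements", and section 3 (Study design) says "post-intervention testing will be conducted in week 7". Section 5e (Data analyses) plans to report proportions and set adherence and retention against the bands. It does not say how adherence is aggregated over participants.

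**The concern.** The word 'offered' sits beside a note that later sessions are not available until earlier ones have been watched. Taken literally, a session that never opened was never offered. The denominator would then shrink with the numerator, and someone who gave up early would look adherent.

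Retention would not always expose this. It counts attendance at follow-up measurements, and nothing visible makes the week 7 visit depend on sessions done. A participant could stop exercising, attend week 7 and count as retained. The error could run only one way, because k/(k+1) is never below k/18. At stake is the decision to go on to a larger study, since the same data could give green on one reading and red on the other.

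**Working it through.** **Inputs.** Three sessions a week for six weeks (5c); bands with edges at 50% and 75% (5a); N = 34, 90% power, one-sided alpha 0.05 (5a); sequential release of sessions (5d). The stopping patterns below are assumptions, because the protocol gives none.

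**1. The plan's own figure.** With p0 = 0.50 and p1 = 0.75, the one-sample normal approximation gives

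n = [(1.645 × √(0.50 × 0.50) + 1.282 × √(0.75 × 0.25)) / 0.25]² = 30.4.

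With continuity correction, n/4 × (1 + √(1 + 2/(n × 0.25)))² = 34.2. N = 34 is reproduced. It depends on the band edges and not on how sessions are counted.

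**2. Planned sessions.** 3 × 6 = 18 per participant, and 34 × 18 = 612 for the study.

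**3. The two readings for one participant.** The unlocked reading is k/(k+1) for k below 18. It counts the next open session as offered and assumes that watching a video equals completing a session.

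| Sessions done (k) | Unlocked | Out of 18 |
|---|---|---|
| 1 | 50.0% (red) | 5.6% (red) |
| 2 | 66.7% (amber) | 11.1% (red) |
| 3 | 75.0% (green) | 16.7% (red) |
| 9 | 90.0% (green) | 50.0% (red) |
| 10 | 90.9% (green) | 55.6% (amber) |
| 13 | 92.9% (green) | 72.2% (amber) |
| 14 | 93.3% (green) | 77.8% (green) |

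The readings disagree about green for 3 to 13 sessions and agree from 14 upward.

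**4. The two readings for a cohort.**

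- Stopping points spread evenly over 0 to 18. The unlocked mean is (18 − H18 + 1)/19 = 15.505/19 = 81.6%, where H18 = 1 + 1/2 + … + 1/18. Out of 18, the mean is 50.0%.
- Ten finish and 24 stop after three. Unlocked: mean (10 × 1 + 24 × 0.75)/34 = 82.4%, or pooled 252/276 = 91.3%. Out of 18: 252/612 = 41.2%. Retention is 10/34 = 29.4% if all 24 are lost, and 26/34 = 76.5% if 16 of them attend week 7.
- All 34 stop after three and 26 return. Unlocked: 102/136 = 75.0%. Out of 18: 102/612 = 16.7%. Retention is 76.5%.

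The choice of reading would therefore matter, which leaves the question of which one the protocol supports.

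**5. What the protocol supports.**

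- *Dose.* Section 5c gives every programme the same fixed course. It allocates content by calendar weeks (1-2, 3-4, 5-6), and the environmental comparison in section 2 uses the same schedule of three trips a week for six weeks. What is offered is a course of 18 sessions.
- *Monitoring.* Under Monitoring of exercise intervention (5c), four days without a session prompts an email. If there is no reply after two more days, a telephone call follows to find out why adherence is low. Under k/(k+1) a pause changes nothing: someone stalled at nine sessions stays at 9/10 = 90% to the end of week 6. Out of 18, the same person ends at 50%. Only the fixed denominator matches this use of the word.
- *Bands.* On the unlocked reading, anyone who does one session scores at least 50%. If all 34 did at least one, the study mean would be in the red band only if virtually all stopped after exactly one. If the others stopped after three, a third of the cohort would have to do none at all: 0.75 × (1 − 1/3) = 50%. A stop band that can hardly be reached is an unlikely intention.
- *Position of the note.* The unlocking note follows the phrase on counting completed sessions. It reads naturally as the reason why a platform count is a usable numerator: sessions cannot be skipped.

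**6. Aggregation.** With 18 for everyone, the pooled proportion and the mean of participant proportions are the same number. The missing aggregation rule then makes no difference between those two.

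**The case for a change.** The best argument for a change is that a go/stop criterion should not rest on inference. The number 18 appears nowhere, the unlocking note stands inside the definition itself, and one sentence would settle the matter. Redacted programme text cannot be checked, although the definition and the analysis section are not redacted. All of this is true, and writing 18 would do no harm. It would record what an analyst would do anyway, without correcting a rule that gives a wrong answer.

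One part stands on its own: the plan does not say how sessions after withdrawal count. Take ten finishers and 24 who stop after three, of whom 16 attend week 7 and eight withdraw. Charging everyone 18 sessions gives 252/612 = 41.2%. Charging the eight only the three they did gives a pooled 252/(26 × 18 + 8 × 3) = 252/492 = 51.2%, or a mean of (10 + 16 × 3/18 + 8)/34 = 60.8%. That moves the result from red to amber, never to green, in a deliberately extreme pattern. Either handling is a legitimate definition, and retention reports drop-out separately. The 16 who stop exercising but return have not withdrawn, so their missed sessions count against 18 either way. They are the group that retention cannot see.

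The claim that 3 to 13 sessions scores green is also looser than it sounds. The bands apply to the study's adherence, and the plan does not classify individual participants.

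**Conclusion.** The concern does not call for a change. The gap is real but small: a number that follows from the protocol by multiplying three by six is not written beside the definition. The large differences (82% against 50%, or 75% against 17%) arise only if 'offered' is read as 'unlocked', and the dose, the monitoring rule, the bands and the position of the note all count against that reading. On the natural reading the inflation is zero, and at study level the green threshold is 0.75 × 612 = 459 completed sessions.

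This rests on two assumptions: that the redacted programme text does not define 'offered' differently, and that adherence is reported for the 34 consented participants on whom the sample size is based. Handling of sessions after withdrawal, and any participant-level confidence interval, are choices left to the analyst. Section 5e plans a descriptive report in which they can be stated.

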The exercise prescription has been designed to achieve World Health Organisation physical activity guidelines for 75 minutes of vigorous intensity activity per week, whereby 25 minutes of vigorous intensity

exercise per session (excluding 'set rest') performed thrice weekly equals 75 minutes per week. Short 20-second rest intervals have been selected so recovery is incomplete between exercises resulting in sustained intensity across the entirety of the aerobic and resistance exercise sections. Such an approach is adapted from Tabata training and repeated sprint training principles, but utilising multi-modal exercises as compared with uni-modal cycling or running-based exercise typically used in Tabata/repeated sprint training.

Table 2. Summary of exercise prescription

	Number of exercises	Sets	Exercise interval	Exercise intensity (RPE /10)	Rest interval (seconds)	Set rest (seconds)
Warm-up	6	1	2-6 reps	2-3	-	-
Aerobic	5	3	40s	5-10	20	50
Resistance	5	2	40s	5-10	20	50
Respiratory	2	1	3 reps	-	5	30

Progression of the intervention

Monitoring of exercise intervention

Immediately after completing the aerobic exercise section, participants will be asked to report their overall RPE for aerobic exercise. The same process will be repeated immediately after the resistance exercise section. Participants will be asked to select the most appropriate score from 0-10 following the standardised prompt: "How much effort/exertion did you put into the workout? Where 0 would be no effort/exertion, and 10 would be the most effort/exertion you could possibly give."

Monitoring of participant engagement will also be conducted using the 'back-end' data from PreActiv's digital platform.

- **Adherence:** If participants have not performed a session in the past four days, a researcher will email them to remind them to log-in and complete their sessions. If there is no response to the

email after two days, a researcher will telephone the participant to explore reasons for low adherence and provide support to increase adherence.

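### As scored, the duration-compliance proportion can include sessions reported as incomplete, and the component proportions do not give the share of sessions completed as prescribed

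*Combined protocol and SAP*

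**What the plan says.** Compliance is one of the eight primary feasibility outcomes. Section 2 and section 5d both define it as a single proportion, that of sessions completed as prescribed. Section 5d then splits it into three components, each with its own reported figure.

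- **Intensity.** Rating of perceived exertion (RPE) is compared with the 5-10 target. "The proportion of aerobic and resistance sessions that are completed at the target intensity will be reported".
- **Type.** After each session the participant answers *all*, *most*, *some* or *none*. Anyone not answering *all* is asked to pick the uncompleted exercises from a list. "Any sessions where ≥ 1 exercise was not completed will be deemed non-compliant to the type of exercise prescribed". The reported figure is: "The proportion of sessions where all exercises are completed will be reported".
- **Duration.** The same question and list are used. "If they do not select any specific exercise, then we infer that participants were unable to perform the exercises for the required duration". The failure rule is: "Any sessions where most / some / none is reported with no specific exercise identified will be deemed non-compliant to duration". The reported figure is: "The proportion of sessions where exercises were performed for the target duration will be reported".

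Section 5e says that feasibility is assessed by reporting proportions, with progression criteria for adherence and retention only. Neither 5d nor 5e gives a rule that combines the three components within a session.

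**The concern.** The duration rule is triggered by a blank list, not by time lost. A participant who answers *none* and ticks every exercise meets no duration-failure rule. One who answers *most* and ticks nothing fails, however little time was lost. The label promises something else: sessions in which the exercises were performed for the target time. A reader of the pilot report would probably take it as evidence that the prescribed dose was delivered.

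The second part concerns the outcome as defined. Three marginal proportions do not show how many sessions met all the requirements together, because the overlap between completion and RPE is not reported.

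What is at stake is the accuracy of a descriptive primary outcome that will inform a larger study. No progression decision depends on it.

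**Working it through.** **1. The prescribed time (section 5c, Exercise dose, and Table 2).** Aerobic: 5 exercises × 3 sets × (40 + 20) s = 15 min. Resistance: 5 × 2 × 60 s = 10 min. The total is 25 min per session, and 3 × 25 = 75 min per week. This reproduces the protocol's own statement of 25 minutes of vigorous "exercise per session (excluding 'set rest') performed thrice weekly equals 75 minutes per week". The warm-up and the breathing exercises lie outside these minutes. Section 5d does not tie its target duration to the 25 minutes, so they serve here only as a yardstick.

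**2. The duration rule applied to single sessions.** Assume that a named exercise was missed in all its sets.

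| Session as reported | Vigorous minutes done | Fails duration? |
|---|---|---|
| One aerobic exercise named | 25 − 3 = 22 (88%) | No |
| All five aerobic exercises named | 25 − 15 = 10 (40%) | No |
| *None*, with all ten aerobic and resistance exercises named | 0 | No |
| *Most*, with nothing named | Unknown, possibly close to 25 | Yes |

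The first three sessions all fail type.

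**3. The rule applied to the proportion.** Let q be the share of attended sessions not answered *all*, and f the share of those that name an exercise. Count a session as duration-compliant unless the failure rule applies to it.

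- Duration proportion = 1 − q(1 − f)
- Share answering *all* = 1 − q
- Difference = q × f

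The documents give neither q nor f. The values below are assumptions that show the range.

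| q | Share answering *all* | Duration at f = 0 | f = 0.5 | f = 1 |
|---|---|---|---|---|
| 0.10 | 90% | 90% | 95% | 100% |
| 0.20 | 80% | 80% | 90% | 100% |
| 0.40 | 60% | 60% | 80% | 100% |

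The excess is zero if no incomplete session names an exercise. If every one does, the duration proportion is 100% whatever was done.

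**4. Can the share answering *all* be recovered?** Yes, but only if the reader knows how type treats a blank list, which 5d does not say. Take q = 0.20 and f = 0.5, where duration is 90%.

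- If type fails only when an exercise is named: type = 1 − 0.20 × 0.5 = 90%, and the share answering *all* is 90% + 90% − 100% = 80%.
- If type fails for every answer other than *all*: type = 80%, which is already the share wanted.
- If the wrong formula is used, the result is 90% (first case read directly) or 80% + 90% − 100% = 70% (second case). Either is 10 points out.

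**5. Can the share completed as prescribed be recovered?** It requires *all* (C), aerobic RPE on target (A) and resistance RPE on target (R) in the same session. Suppose that A and R are reported separately, which is the more informative reading. The joint share then lies between max(0, A + R + C − 2) and min(A, R, C).

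- Each at 80% (assumed): 2.4 − 2 = 40% up to 80%. Under independence, 0.8³ = 51%.
- Each at 90% (assumed): 2.7 − 2 = 70% up to 90%. Under independence, 0.9³ = 73%.

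The reported proportions therefore do not fix the joint share, even once C is known.

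**The case against.** The best defence is that type and duration sort incomplete sessions by reason. A named exercise is a type problem. No named exercise is taken as a duration problem, and the protocol openly calls that an inference. On this reading every incomplete session fails exactly one of the two components, so none escapes. This stands as an account of the intention, and the fix keeps the distinction. It does not make the duration label accurate.

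Second, 5d gives only a failure rule and never says outright that named-exercise sessions count as compliant with duration. That is correct. A reader might infer that the plan deliberately credits incomplete sessions with full duration, but the text does not support that. It leaves their status unstated, and the rule and the label point in different directions for these sessions.

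Third, the definition of compliance leads straight into the three components, so component-wise reporting is a legitimate reading, and 5e promises no composite. This also stands. The joint proportion is therefore proposed alongside the components, not as a replacement for them.

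Fourth, every percentage above rests on assumed inputs. That is true. What is secure is the algebra, not any particular size.

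**Conclusion.** The point holds and is minor. Applied as written, the duration rule yields a proportion that can include sessions reported as incomplete, and it exceeds the share answering *all* by q × f. Both quantities are unknown, so the excess may be zero. The conclusion assumes that a session not failed on duration is counted as compliant, which is the natural reading but is not stated. Separately, the component proportions do not determine the share of sessions completed as prescribed. With three components at an assumed 80% each, it could be anywhere from 40% to 80%.

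Two stronger conclusions are not supported. A reader might infer that the feasibility decision is compromised. It is not: compliance has no progression threshold, the criteria concern adherence and retention, N = 34 does not depend on compliance, and the affected sessions still fail type. A reader might also infer that duration should fail for every answer other than *all*. Nothing in the documents requires that. It would remove the protocol's distinction between reasons, and it would fail on duration a session in which only a breathing exercise was missed.

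**What to change.** In section 5d:

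1. Do not report incomplete sessions with a named exercise as performed for the target duration. Relabel the present measure *incomplete, no exercise identified*, and tabulate incomplete sessions by exercise named versus none named.
2. Alongside the components, report one joint proportion over attended sessions: answered *all*, with aerobic and resistance RPE both within the protocol's own 5-10 target. Show the number of sessions with a missing RPE.
3. State whether an answer of *most*, *some* or *none* with a blank list fails type.

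The cost is some rewording, one derived variable and one small table, all from data already being collected. The downside is that reported compliance will be lower, since a joint proportion cannot exceed its smallest component.
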